## 8. STUDY DESIGN

### 8.1. Overall Study Design and Plan

This is a Phase 3, multinational, multicenter, randomized, double-blind, placebo-controlled study in subjects experiencing an acute exacerbation of schizophrenia. Subjects will be screened up to 10 days prior to randomization. Upon completion of screening assessments, subjects meeting eligibility criteria will be admitted to an inpatient unit on Day -1, if they are not already inpatient. Currently prescribed antipsychotics will be discontinued at screening.

Study design and timeline are summarized in the schematic shown in [Figure 1](#).

On Day 1 (Visit 2), subjects meeting eligibility criteria will be randomized in a 1:1:1 fashion to one of the following 3 treatment groups: ALKS 3831, olanzapine, or placebo, and will receive double-blind treatment for up to 4 weeks.

On Days 1 and 2, subjects randomized to ALKS 3831 will receive 10/10 [10 mg olanzapine/10 mg samidorphan] and subjects randomized to olanzapine will receive 10 mg. On Day 3, the dose will be increased to 20/10 [20 mg olanzapine/10 mg samidorphan] for subjects randomized to ALKS 3831 or 20 mg for subjects randomized to olanzapine. Following the increase on Day 3, the dose may be decreased to 10/10 (ALKS 3831) or 10 mg (olanzapine) at end of week 1 (Day 7) or week 2 (Day 15) if there are tolerability problems based on judgment of the investigator. No further dose adjustments will be allowed Day 15 onward for the remaining 2-weeks of the treatment period. All subjects will receive 1 capsule daily in a blinded manner.

Subjects are required to be inpatient for the first 2 weeks of the treatment period (until Day 15). Following the mandatory 2-week inpatient stay, subjects can either continue the study as inpatients for the full 4-week treatment period or be discharged at the end of Week 2 or end of Week 3 if they meet the discharge criteria specified in [Section 8.1.1](#).

[figure not shown]
Following discharge, subjects will be contacted by study staff at least once between their weekly site visits to monitor their status and determine if there are any safety concerns that would precipitate re-admission to the inpatient facility. If subjects are re-admitted to the inpatient facility due to safety concerns, it will be recorded as an SAE.

Subjects completing 4 weeks of treatment with study drug will be eligible to continue in the open-label, long-term safety study (ALK3831-A306) and receive ALKS 3831 for up to 52 weeks. Subjects not continuing in the long term safety study will enter a 2-week safety follow-up period. During this follow-up period subjects may be treated with any antipsychotic medication according to physician recommendations.

Subjects who are inpatient at the end of the 4-week treatment period and are not continuing in the extension study (ALK3831-A306) may continue as inpatients for up to 1 additional week of the 2-week safety follow-up period. These subjects may be discharged from the inpatient unit at any time during this week based on investigator's judgment. For subjects continuing in the safety extension study (ALK3831-A306), details regarding the additional inpatient week will be provided in the ALK3831-A306 protocol.

The total duration of this study is approximately 7.5 weeks, including a 10-day screening period (Days -10 to -1), a 4-week treatment period (Days 1-29), and 1 follow-up visit 2 weeks after EOT (Day 43).

**Figure 1: Study Design Schematic**

### 8.1.1. Discharge Criteria

Subjects are eligible to be discharged at end of Week 2, Week 3, or Week 4 if they meet ALL of the following criteria:

1. Subjects are judged clinically suitable for discharge by the investigator:
  - a. Subjects have shown a sustained pattern of improvement relative to their condition on Day 1 within the past week.
  - b. Subjects are not a danger to themselves or others
  - c. Subjects can be discharged into a supervised living environment deemed suitable by the investigator.
2. Subjects show stabilization of symptoms as confirmed by PANSS:
  - a. PANSS total score <70
  - b. Score <4 on selected PANSS positive items (Item 1 [P1; delusions], item 2 [P2; conceptual disorganization], item 3 [P3; hallucinatory behavior], and item 6 [P6; suspiciousness/persecution])
3. Subjects answer “No” on items 4 or 5 of the Columbia-Suicide Severity Rating Scale (C-SSRS-ideation), and “No” to all 5 items of (C-SSRS-behavior)

Subjects not meeting the discharge criteria will continue as inpatients for the remainder of the study and for up to 1 additional week if they do not meet discharge criteria at EOT.

## **8.2. Schedule of Visits and Assessments**

The schedule of visits and assessments is shown in [Table 1](#).

For a missed visit, the site should attempt to contact the subject to reschedule.

Premature discontinuation procedures are provided in [Section 7.3](#).

**Table 1: Schedule of Visits and Assessments**

Period	Screening	Double-Blind Treatment Period					Follow-Up 
Visit Number	1	2	3	4	5	6	7
Study Day	-10 to -1	1	8	15	22 	29/ET 	43 
Informed Consent	X						
Demographics	X						
Medical/ Psychiatric History	X						
Mini International Neuropsychiatric Interview (MINI)	X						
Eligibility Criteria Review	X	X 					
Genotype Sample	X						
Height	X						
Weight and waist circumference (conducted 3 times each visit)	X	X 				X	X
Physical Exam 	X	X 				X	X
Randomization		X					
Urine Drug Screen 	X	X 			X 	X 	
Pregnancy Testing	X	X 					
Serology Testing 	X						
Laboratory Samples  (refer to Table 2 )	X	X 		X		X	
PK Sample 		X 		X		X	
Vital Signs 	X	X 	X	X	X	X	X
12-Lead Electrocardiogram	X	X 	X	X	X	X	X
Adverse Event Monitoring	X	X	X	X	X	X	X

**Table 1: Schedule of Visits and Assessments (Continued)**

Period	Screening	Double-Blind Treatment Period					Follow-Up 
Visit Number	1	2	3	4	5	6	7
Study Day	-10 to -1	1	8	15	22 	29/ET 	43 
Concomitant Medication Review	X	X	X	X	X	X	X
Columbia-Suicide Severity Rating Scale (C-SSRS) 	X	X 	X	X	X	X	X
Abnormal Movement Scales 		X 	X	X	X	X	X
Positive and Negative Syndrome Scale (PANSS) 	X	X 	X	X	X	X	
Modified Overt Aggression Scale 		X	X	X	X 	X 	
Clinical Global Impression – Severity (CGI-S)	X 	X	X	X	X	X	
Clinical Global Impression – Improvement (CGI-I)			X	X	X	X	
Informed Consent for ALK3831-A306						X 	
Emergency treatment card 		X				X	
Admission to Inpatient Unit 	X						
Discharge from Inpatient Unit 				X	X	X	
Study Drug Dispensation 		X	X	X	X		
Study Drug Return and Adherence Review			X	X	X	X	

 Follow-up Visit (V7) is not required for subjects who enroll in ALK3831-A306 A visit window of ±2 days (anchored to Day 1) is allowed Predose Full physical exam at screening; brief physical exam at all subsequent time points.

-  Urine drug screen via dipstick at screening and prior to randomization on Day 1. Drug screen at Visits 5 and 6 applies to outpatient subjects only. Urine drug screen includes opiates, phencyclidine (PCP), amphetamine/methamphetamine, and cocaine.
-  For outpatient subjects only
-  Serology testing includes anti-human immunodeficiency virus (HIV) antibody, hepatitis B surface antigen, and anti-hepatitis C antibody.
-  Subjects must fast (no food or drink except water) for at least 8 hours before lab draws. Lab draws are to be conducted in the morning for all specified visits.
-  One PK sample will be collected at the specified visits to measure plasma levels of olanzapine, samidorphan, and metabolites of interest
-  Vital signs include orthostatic blood pressure and heart rate, respiratory rate, and oral body temperature. Blood pressure, pulse rate, and respiratory rate will be taken after the subject has been supine for 5 minutes and once again after the subject has stood for 2 minutes.
-  The “Baseline/Screening” version of the C-SSRS will be used at screening; the “Since Last Visit” version to be used at all other scheduled visits.
-  Abnormal movement scales include the following: Abnormal Involuntary Movement Scale (AIMS), Barnes Akathisia Rating Scale (BARS), and Simpson-Angus Scale (SAS).
-  With the exception of the screening visit, the PANSS should be administered before other psychiatric assessments at each specified study visit.
-  The MOAS will be performed on all subjects at Visits 2, 3 and 4 and only on inpatient subjects at Visits 5 and 6.
-  Only for inpatient subjects
-  CGI-S will be administered at the Screening Visit using the structured interview guide for global impressions (SIGGI)
-  The informed consent form for the open-label extension, ALK3831-A306, must be distributed to subjects by the end of treatment. However, the form may be distributed to subjects earlier at the investigator's discretion.
-  Emergency treatment card to be dispensed at randomization (Visit 2), confirmed at subsequent time points, and collected at Visit 6, EOT.
-  Subjects will be admitted to the inpatient unit on the same day as their screening assessments if they are not already inpatient.
-  Subjects may be discharged at Day 15, Day 22, or Day 29 if they meet discharge criteria. Subjects not meeting discharge criteria at Day 29 may remain inpatient for up to 1 additional week and may be discharged from the inpatient unit at any point during this week at the investigator's discretion.
-  During the inpatient stay, study drug will be administered daily by study staff, preferably at bedtime. Upon discharge, subjects will be given study drug to take daily, preferably at bedtime though dose timing may be adjusted at the investigator's discretion based on tolerability.

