### 7.3. Subject Withdrawal

A subject may be discontinued from the study at any time if the subject, investigator, or sponsor determines that it is not in the best interest of the subject to continue participation. Reasons for discontinuation include:

- Adverse Event
- Lack of Efficacy
- Lost to Follow-up
- Withdrawal by Subject
- Protocol Deviation (non-compliance with study drug or study procedures)
- Pregnancy
- Study Terminated by Sponsor
- Other

Additionally, if a subject has an  $ANC < 1.0 \times 10^3 \mu L$  or  $HbA1c \geq 6.5\%$  at any time from Visit 2 to Visit 6, the PI (or designee) should discontinue the subject from participation immediately.

If a subject withdraws from the study for any reason, any ongoing AEs will be followed until resolution, until deemed stable by the investigator, or until the subject is deemed by the investigator to be lost to follow-up. If, in the opinion of the investigator, it is necessary to monitor a subject beyond the safety follow-up visit, the follow-up period may be extended as necessary. In such instances, the sponsor and the investigator will agree to an acceptable follow-up schedule.

In the event that a subject chooses to withdraw from the study, the investigator should make a reasonable effort to ascertain the reason(s) for withdrawal, while fully respecting the subject's rights. Randomized subjects are to be asked to return to the clinic for an early termination (ET) visit and to complete a subsequent safety follow-up period. The early termination visit should be scheduled as close as possible to the subject's last dose and will mimic the assessments scheduled to be conducted at Visit 6. If the subject fails or refuses to return to the study center, an attempt must be made to contact the subject by telephone in order to assess as many safety and efficacy parameters as possible. All data collected over the telephone must be documented and kept in the subject's record.

The investigator must maintain a record of all subjects who fail to complete the study. A full explanation of the reason for study discontinuation will be made on the appropriate electronic case report form (eCRF).

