#### **8.3.16. Emergency Treatment Card**

An emergency treatment card will be distributed to each subject and collected from each subject at the time points indicated in [Table 1](#). The card will indicate that the subject may be receiving an opioid antagonist and/or olanzapine and will include the PI's contact information, a suggested pain management plan and information regarding opiate blockade. Subjects will be instructed to keep the card with them at all times. Study personnel will confirm that subjects have the card in their possession at each study visit indicated in [Table 1](#).

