#### **8.4.5. Pain Management**

Because ALKS 3831 contains samidorphan, a  $\mu$ -opioid receptor antagonist, patients may experience reduced or ineffective analgesia when taking an opioid analgesic agent concurrently with ALKS 3831, including several days after last dosing of ALKS 3831.

In the event of an emergency, pain management of the subject should include the following:

- Regional analgesia or use of non-opioid analgesics
- If opiate anesthesia or analgesia is required, the subject should be continuously monitored, in an anesthesia care setting, by persons not involved in the conduct of the surgical or diagnostic procedure. The opioid therapy must be provided by individuals specifically trained in the use of anesthetic drugs and the management of the respiratory effects of potent opioids, specifically the establishment and the maintenance of a patent airway and assisted ventilation
- Close monitoring by appropriately trained personnel in a setting equipped and staffed for cardiopulmonary resuscitation

For subjects requiring emergency opioid analgesics prior to dosing, the study drug should not be administered. If opioid analgesics are required after the study drug has been dosed, it may take several days for opiate sensitivity to be restored, since samidorphan is an opioid antagonist and could interfere with opioid-mediated pain management.

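### The emergency treatment card is taken back at end of treatment, although section 8.4.5 says opioid blockade may persist for several days after the last ALKS 3831 dose

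*Protocol*

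**What the plan says.** On the card:

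- Protocol Table 1 marks the card at Visit 2 and in the Day 29/ET column only. There is no mark at Visit 7. Footnote 18 reads: "Emergency treatment card to be dispensed at randomization (Visit 2), confirmed at subsequent time points, and collected at Visit 6, EOT".
- Section 8.3.16 has the card given to and collected from every subject at the Table 1 time points, and tells subjects to carry it at all times. On content: "The card will indicate that the subject may be receiving an opioid antagonist and/or olanzapine". It also holds the investigator's contact details, "a suggested pain management plan and information regarding opiate blockade".

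On how long blockade lasts, section 8.4.5 makes two statements:

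- Analgesia from an opioid may be reduced or ineffective when it is taken with ALKS 3831, "including several days after last dosing of ALKS 3831".
- If opioids are needed once study drug has been dosed, "it may take several days for opiate sensitivity to be restored".

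On timing:

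- Table 1 dispenses no study drug at Visit 6. Footnote 8 says: "Lab draws are to be conducted in the morning for all specified visits". Footnote 21 says: "During the inpatient stay, study drug will be administered daily by study staff, preferably at bedtime". Bedtime is also preferred after discharge.
- For withdrawals, section 7.3 says the "early termination visit should be scheduled as close as possible" to the last dose, sets no limit, and asks the subject to complete the safety follow-up period.
- Under section 8.1, subjects not entering ALK3831-A306 have a two-week follow-up ending at Visit 7 (Day 43). Those still inpatient at end of treatment may stay up to one more week.

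**The concern.** The card exists because blockade can make ordinary emergency analgesia fail. If opioids are unavoidable, section 8.4.5 asks for continuous monitoring in an anesthesia setting, staff trained to manage opioid respiratory effects, and resuscitation capability. Emergency staff who do not know of the blockade have no reason to take those steps.

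The protocol names a hazard that outlasts dosing, yet withdraws the carried warning as that period begins. No passage delays collection, replaces the card or describes another carried warning. Following the plan exactly therefore removes an existing safeguard too early for some subjects. What is at stake is patient safety at a low level of risk.

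**Working it through.** The plan gives no figure to reproduce, so the check is a comparison of texts followed by rough arithmetic on declared assumptions.

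**Who loses the card, and when**

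1. *Completers.* Footnote 18 and the Table 1 row collect the card at Visit 6. With bedtime dosing and a morning visit, the last dose was the night before. Assuming a dose at 21:00–24:00 and a visit at 08:00–12:00, the gap runs from 8 h (24:00 to 08:00) to 15 h (21:00 to 12:00).
2. *Early terminators.* Collection follows from the 29/ET column together with section 7.3. The gap may be shorter or much longer than for completers.
3. *Not affected.* Subjects who stay inpatient through the blockade period, early terminators who return after it has ended, and those who never return and so keep the card. Subjects entering ALK3831-A306 are outside this point.

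**Blockade time left after collection**

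The protocol gives no number of days, so 2–7 days is assumed.

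- Completers: 2 d − 15 h = 1.375 d, up to 7 d − 8 h = 6.67 d; midpoint about 4.0 d.
- Early terminators: 0 d (late visit) to 7 d (same-day visit); midpoint 3.5 d.

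**Subjects on ALKS 3831**

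From the documents: 130 planned per group (protocol synopsis; SAP section 2) and 30% dropout (protocol section 14.1). Assumed: dropout could range over 20–40%, and 10–50% of completers do not roll over.

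| Dropout | Early terminators | Completers | Plus 10–50% not rolling over | Total |
|---|---|---|---|---|
| 20% | 26 | 104 | 10.4–52 | 36–78 |
| 30% | 39 | 91 | 9.1–45.5 | 48–85 |
| 40% | 52 | 78 | 7.8–39 | 60–91 |

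These counts have not been reduced for subjects who stay inpatient or never return.

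**Expected opioid-requiring emergencies in the window**

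Assumed yearly rate 5–20%, midpoint 12.5%. Expected number = person-days ÷ 365.25 × rate.

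- Mid-range, 30% dropout and 30% not rolling over: 39 × 3.5 + (91 × 0.30 = 27.3) × 4.0 = 136.5 + 109.2 ≈ 246 person-days = 0.67 person-years. Then 0.67 × 0.125 ≈ 0.08.
- All inputs at their low end: 7.8 × 1.375 = 10.7 person-days = 0.03 person-years. Then 0.03 × 0.05 ≈ 0.001.
- All inputs at their high end: 52 × 7 + 39 × 6.67 ≈ 624 person-days = 1.71 person-years. Then 1.71 × 0.20 ≈ 0.34.

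These are emergencies, not harms; the missing card would also have to change the care given.

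**The case against.** The strongest case against is that this is a low-risk matter resting partly on inference and on documents outside the package. Its parts fare as follows.

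- *Both sentences in section 8.4.5 describe the period after the last dose.* A reader might infer this, but only the first refers to last dosing. The second applies after any dose. The first is enough for the point, though it gives no number of days.
- *Footnote 18 orders collection at early termination.* It does not; it names Visit 6, EOT. Section 7.3 says the early termination visit repeats the Visit 6 assessments, and returning a card is not clearly an assessment. The 29/ET column heading supports the reading, so it stands as an inference.
- *The protocol contradicts itself.* It does not. A site can follow both instructions; the fault is a gap in cover.
- *Subjects leave uninformed.* The documents do not show this. The card template and consent text are not in the package and either may give post-dose advice. Section 17.3 gives the subject a copy of the consent form but does not describe it as carried.
- *Other safeguards cover the window.* Partly. The extra inpatient week may span most or all of a 2–7 day blockade, and treatment is inpatient until Day 15, so some early terminators start from a ward. But the extra week is optional and can end at the investigator's discretion (footnote 20). Supervised discharge (section 8.1.1, item 1c) is not stated to apply to early terminators or to that discretionary discharge. Caregivers are required only at some sites, and neither supervisor nor caregiver is described as holding the pain plan. Exclusion criterion 13 covers anticipated opioid need, not emergencies.
- *About 0.3 emergencies should be expected.* That figure stacks every extreme and removes no inpatients. It is a bound under the assumptions, not an estimate.

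**Conclusion.** The gap is real on the text. For subjects who leave at or soon after Visit 6 or early termination without entering ALK3831-A306, the card is collected while, by section 8.4.5, blockade may still be present. For completers this rests on the explicit collection rule; for early terminators, on the 29/ET column and section 7.3.

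The consequence is small: on the order of 0.1 opioid-requiring emergencies or fewer in the whole trial under mid-range inputs. The length of blockade, the non-rollover share, the emergency rate and the clock times are assumptions without a source in the documents. Confidence is high in the scheduling fact and lower in the safety consequence, given the unseen card and consent text. Nothing here touches the estimand, power or analysis. It merits a cheap, low-priority correction because the hazard is one the protocol itself names and the safeguard already exists.

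**What to change.** In Table 1, footnote 18 and section 8.3.16, move card collection from Visit 6/ET to the existing Visit 7 for subjects not entering ALK3831-A306. At Visit 6/ET, in all arms so that the blind is unaffected, have the site write on the card the last-dose date and the number of days after it during which blockade may persist. The sponsor must supply that number, since the protocol gives none.

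Cost: one mark moved, two texts reworded and two entries per card, with no new visit or procedure.

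Downsides: some cards will not come back, and the card outlasts the blockade. With the ±2-day windows, Visit 7 (Days 41–45) falls 10–18 days after Visit 6 (Days 27–31) for completers. The card is then held from 10 − 6.67 ≈ 3 days to 18 − 1.375 ≈ 17 days beyond an assumed 2–7 day blockade. Two holders in three never had samidorphan. The written end point limits needless avoidance of opioids but does not exclude it.

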### **8.3. Study Procedures Descriptions**

Details of the study procedures are described below. The overall schedule of assessments is provided in [Table 1](#).

#### **8.3.1. Informed Consent**

The nature of the study and its risks and benefits will be explained to the subject by the principal investigator or designated study personnel as outlined in [Section 17.3](#).

Prior to the administration of any study-specific procedures, authorized study personnel will obtain written informed consent from each potential subject.

#### **8.3.2. Eligibility Review**

An eligibility review will be conducted by the investigator at the visits specified in [Table 1](#) using the subject inclusion criteria in [Section 7.1](#) and exclusion criteria in [Section 7.2](#).

#### **8.3.3. Demographics and Medical History**

Subject's demographic data and medical history will be reviewed and documented at the time point(s) specified in [Table 1](#).

#### **8.3.4. Concomitant Medication Review**

All medications (prescription and non-prescription, including vitamins and herbal supplements) taken by a given subject within 60 days of screening through follow-up will be recorded.

At each study visit (see [Table 1](#)), the investigator or designee will record the following data on all medications used by the subject: name, dose, regimen, route of administration, start and stop dates, and the indication for use.

#### **8.3.5. Vital Signs**

Vital signs (ie, blood pressure, heart rate, respiratory rate, and oral body temperature) will be assessed at the time point(s) specified in [Table 1](#). An effort will be made to consistently use the same arm (preferably the subject's dominant arm) to measure blood pressure and heart rate throughout the study. The blood pressure cuff will be calibrated per study site standard operating procedures (SOP). Automated measurement is preferred, but if performed manually, heart rate will be measured in the brachial artery for at least 30 seconds. Orthostatic blood pressure, and heart rate will be collected in the following manner:

- Allow subject to be in a supine position for at least 5 minutes
- Measure blood pressure and heart rate
- Have subject stand for 2 minutes
- Measure blood pressure and heart rate

Vital signs may be collected at any time during a scheduled visit, unless otherwise noted.

